	
three, and six months to complete all safety and efficacy assessments.
 
Subjects in the addenda will be followed at one month post-infusion and then at three and six months to complete all safety and efficacy assessments. Patients participating in Addendum B will receive penicillin/streptomycin free cells. If they are participating in Addendum C or D subjects may receive cells with antibiotic (penicillin/streptomycin).
 
All subjects, with the exception of subjects participating in Addendum C, will also have a final twelve-month contact for assessment of vital status and occurrence of hospitalization.

ROUTE OF ADMINISTRATION	Peripheral Intravenous Infusion
DURATION OF STUDY PARTICIPATION	
Pilot phase (15 subjects)
 
12 months (Follow-up will be at 2 weeks, 1, 3, 6, and 12 months) for the first infusion.
 
Pilot subjects will have an optional additional 12-month follow-up period for a second infusion (Reference Addendum A), and up to two (2) additional infusions with a 6 to 12-month follow-up period under Addendum C. The follow-up will be at 1, 3, 6, and 12 months for Addendum A. The follow-up for Addendum C will be at 1, 3, and 6 and/or at 12 months.
 
Randomized phase (30 subjects)
 
12 months (Follow-up will be at 2 weeks, 1, 3, 6, and 12 months.)
 
Subjects that received placebo will have the option to receive a single infusion of allogeneic MSCs under Addendum D. The follow-up will be at 1, 3, 6, and 12 months for these subjects.
 
Addendum B sub-study (20 subjects)
 
Subjects in the penicillin/streptomycin free addendum (Reference Addendum B) will have up to a 12-month follow-up schedule at 1, 3, 6, and if applicable, 12 months. Subjects continuing with the additional infusions in Addendum C will have up to a 12-month follow-up schedule at 1, 3, 6, and if applicable, 12 months for each additional infusion. Subjects will receive one initial infusion (Addendum B) and can receive up to three (3) additional infusions under Addendum C for a total of four infusions.

SUBJECT POPULATION	Forty-Five (45) subjects with frailty will be enrolled in the main study.

	An additional 20 subjects will be included in a sub-study, (Please see Addendum B).

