The Month 12 visit will be waived if screening visits for subsequent infusions take place prior to this visit.

B.15 Statistical Considerations

All subjects will be offered the penicillin/streptomycin free hMSCs and formal statistical considerations regarding sample size and power are not provided. Based on prior studies, stem cells are safe but strict safety monitoring will be employed to continue the safety assessment of penicillin/streptomycin free allogeneic infusion of MSCs. No detailed analyses will be described in the statistical analysis plan.

B.16 Safety Monitoring of 30-Day Rate of TE-SAEs

Monitoring of the rate of TE-SAEs by 30-days post infusion among subjects who received the infusion of penicillin/streptomycin free allogeneic MSCs will be employed to assist the DSMB in prospective monitoring of this study. The guideline is to be used to indicate boundaries requiring discussion by the DSMB and is designed to assist the independent DSMB in overseeing the study. The DSMB may also request additional interim analyses and develop other criteria including provision for monitoring of potential late effects to determine when to intervene in the enrollment or treatment of subjects in the study. Monitoring of key safety endpoints will be conducted. If rates significantly exceed the pre-set threshold, then the DSMB will be notified.

A Bayesian motivated safety stopping guideline for monitoring the 30-day TE-SAE rate will be used for this trial. The expected underlying rate of TE-SAE at 30 days post-infusion is assumed to be 10% based on the assumption that 2 out of 20 subjects experience a TE-SAE. It would then be assumed that a rate of greater than 40.0% is unacceptable.

A Beta distribution can be used as the prior distribution of θ ; where θ is the proportion of subjects who experience an TE-SAE by 30-days post infusion. The stopping rule is based on the beta-binomial methodology and assumes a prior expected failure rate. This leads to prior Beta parameters where $a=0.8$ and $b=5.2$. The Beta distribution will have a prior mean of 0.13 and a prior probability of <0.05 of exceeding 0.40. The guideline is derived such that there is strong evidence (posterior probability >0.95) that the probability of the event is greater than 40%, the trial will be stopped. The resulting boundaries tabulated in table B2 were rounded to be conservative with the stopping guideline and is considered after 5 subjects are enrolled on the study.

TABLE B2

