This addendum protocol is designed to test the safety of sequential infusions of allogeneic mesenchymal stem cells 6 to 18 months following previous infusion. Subjects in this protocol have previously participated in protocols receiving open label infusions (phase I subjects). There is an important need to assess the safety and immunologic tolerability of additional doses of intravenous allogeneic MSCs in the target population. Previously a group of 12 subjects received two doses delivered 12-18 month apart with excellent safety and no adverse effects attributed to the study agent. A second group of 20 subjects received a single dose of MSCs, in the penicillin/streptomycin free cohort. Subjects receiving either one or two sequential doses have not mounted significant immunologic reactions to the study agent.

Subjects in the pilot phase would have received two (2) of the possible four (4) infusions of allogeneic MSCs and are eligible to participate in this optional follow-on phase. Additionally, subjects receiving one dose (100 Million cells) in the penicillin/streptomycin free protocol are eligible to receive up to three (3) additional infusions. Because several studies, reviewed below, have now shown safety of repeat doses of MSCs in a variety of medical conditions, additional safety testing in the subject population of aging frailty enrolled in the CRATUS trial is required⁹². All study specific processes and procedures included in the pilot phase and penicillin free follow-on phase of the protocol apply in this addendum unless otherwise noted.

Pilot subjects participating in this addendum are eligible to receive up to two (2) additional infusions and subjects participating from Penicillin Free cohort are eligible to receive up to three additional infusions of MSCs (100 Million cells) administered 6 -18 months apart. The MSCs provided to study subjects in this addendum may be penicillin/streptomycin free. Subjects from the Pilot phase returning for their additional infusions may receive cells with penicillin/streptomycin. Altogether, subjects will have received four (4) infusions over a time span ranging approximately 3 to 6 years. Subjects will have ongoing safety monitoring that will include detailed immunologic assessments.

Subjects that do not want an additional infusion will not be eligible to continue in the study and/or receive additional infusions under this addendum.

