C.14 Study Procedures for Optional Additional Infusions for Pilot and Penicillin/Streptomycin Free Subjects (See Table C1)

Table C1: Time and Events Table for Optional Pilot Phase and PCN/Streptomycin Free Additional Infusion(s) Schedule

Visit Schedule for Additional Infusions (repeating for up to 4 doses every 6 -18 months)	Screening - 45 days from baseline	Baseline (-4 weeks)	Day 1	Month 1 (Day 30) (+/- 2 weeks)	Month 3 (Day 90) (+/- 30 days)	Month 6 (Day 180) (+/-30 days)	Month 12 (Day 365) (+/- 2 weeks)
Informed Consent	x						
Full Medical History	x						
Physical Exam	x	x	x	x	x	x	
12-lead (ECG)	x	x	x	x	x	x	
Concomitant Medications	x	x	x	x	x	x	x
Mini Mental State Examination (MMSE)	x					x	
Infusion Treatment (IP)			x				
Dobutamine Stress Echo Test (DSE) ¹²	x					x	
Bone Density Scan (DEXA) ⁸		x				x	
FEV-1		x				x	
6 Minute Walk Test		x				x	
4 Meter Gait Speed Test ⁷		x				x	
SPPB Assessment		x				x	
Dynamometer (handgrip) ⁹		x				x	
Smell Identification Test (UPSIT)		x				x	
IIEF, SQOL-F Questionnaires		x		x	x	x	
QOL Questionnaires (ICECAP, EQ-5D, SF-36,CHAMPS, MFI)		x		x	x	x	
Urinalysis	x			x	x	x	
Hemat, Chem., CBC, LFTs, INR, and other labs ¹	x		x	x	x	x	
HIV 1, HIV 2, Hep. B & C, and CMV	x						
Serum or Urine Pregnancy Test ²	x		x				
Review Adverse Events			x	x	x	x	x
Immune Monitoring ⁴			x	x	x	x	
Biomarker Assessment ³			x			x	
Optional: Brachial Ultrasound ⁵		x			x		
Optional: Endothelial blood samples ⁶		x			x		

Time and Events Table Key:

1 - The minimal laboratory requirements for hematological, liver function and renal function include:

Hematology Tests: white blood cell count, platelet count, hemoglobin and Hematocrit, red blood cell count, CBC with Differential: neutrophils, lymphocytes, monocytes, eosinophils, and basophils.

Liver Function Tests: Albumin, alkaline phosphatase, alanine transaminase, aspartate aminotransferase, prothrombin time / activated partial thromboplastin time, and bilirubin (fractionate if total >1.5 times normal).

Renal Function Tests: creatinine, creatinine clearance, blood urea nitrogen (BUN), glomerular filtration rate, sodium, potassium, chloride, calcium, carbon dioxide, total protein, glomerular filtration rate (GFR) and glucose, (HbA1c) will be collected at every follow-up visit only for subjects diagnosed with diabetes mellitus (DM).

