9 – Dynamometer will be performed at least three (3) times during each applicable visit for each hand. The three values collected will be averaged for each hand. (Please reference the instruction manual on how to administer.)

10– Infectious disease tests – HIV, HIV 2, Hep B (HBsAG, Anti-HBs, Anti-HBc), and Hep C (Anti-HCV), VDRL, Syphilis, West Nile Virus, and CMV. (Conducted within 30 days of infusion, if test expire prior infusion, they must be performed again)

11–Month 12 follow-up phone call may be waived if the subject has a screening visit for an additional infusion prior to this visit.

12 - Guidelines for completing the (DSE) are outlined in Appendix 2 of this protocol.

C.15 Study Visits

C.15.1 Screening Visit for additional infusion

See Table C1 for the procedures and assessments to be performed during the screening visit of the study for the subjects that consent to participate in the additional infusions. Once the subject signs the informed consent form (ICF), the subject will then have a 45-day window from the time the subject signs the ICF to the start of the baseline visit to complete all screening procedures. The tests may take place over several days to complete. No screening exams will take place until the subject is fully informed of the research and signs the consent form.

There will be up to a +/-2 week window from the subjects Month 12 phone call from the subject's previous infusion to begin screening procedures, at which point the month 12 phone call visit from the original infusion will be waived, if screening visits for subsequent infusions take place prior to this visit.

If a dobutamine stress echo was performed within 6 months, that report can be used in place of screening DSE for additional infusions

C.15.2 Baseline Visit for additional infusion

See Table C1 for the procedures and assessment to be performed during the baseline visit of the study. Once all screening exams are completed and it has been determined that the subject remains eligible for the study, subjects will be enrolled into the study. The baseline visit will take place within four weeks of the infusion. The listed procedures should all be performed as soon as practicable. If DEXA was performed within 6 months, that report can be used in place of baseline DEXA for additional infusions.

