See Table C1 for the procedures and assessments to be performed for Month 12 visit. This visit will be conducted via a phone interview with the subject. A phone script will be provided to the study personnel to use when interviewing the subject. There will be a +/- window of 2 weeks for this visit. The Month 12 visit will be waived, if screening visits for subsequent infusions take place prior to this visit.

C.16 Statistical Considerations

All subjects will be offered the re-infusion and formal statistical considerations regarding sample size and power are not provided. Based on prior studies, additional infusions of stem cells are safe but strict safety monitoring will be employed to continue the safety assessment of allogeneic infusion of MSCs. Detailed analyses will be described in the separate statistical analysis plan.

Addendum D: Placebo Group Optional Follow-on Phase

D.1 Rationale and Description of infusion for 10 subjects randomized to placebo group

This addendum protocol is for subjects that have previously participated in the randomized portion of the study and received placebo. Ten (10) subjects are eligible for a single infusion of 100 million allogeneic human mesenchymal stem cells (Reference section 3.2).

Subjects from the randomized phase who previously received placebo infusions and are participating in this addendum will receive one (1) infusion of 100 Million allogeneic hMSCs. The hMSCs provided to study subjects in this addendum may have penicillin/streptomycin. Altogether, subjects in this addendum will have the option to receive one infusion of MSCs for a total of two (2) infusions (1 placebo infusion from the main phase and one infusion of 100 Million hMSCs) once all eligibility criteria have been met.

Subjects will have ongoing safety monitoring that will include detailed immunologic assessments.

D.2 STUDY OBJECTIVES AND ENDPOINTS:

D 2.1 - Study Objectives

D.2.1.1 Primary Objective:

- To demonstrate the safety of intravenous allogeneic hMSCs administered in subjects with Frailty and to explore treatment efficacy (decrease in frailty, frequency of acute exacerbations, change in symptom related quality of life, improved cardiovascular status, decrease in inflammatory biomarkers, endothelial function and 1 year survival).

D.2.1.2 Secondary Objective:

- To explore effects of allo-hMSCs on symptom related quality of life, cardiovascular performance, endothelial function and inflammation.

D.2.2 Study Endpoints

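### In Addenda B and C the Month 12 call is waived on re-screening rather than on re-infusion, so a treated subject who re-screens and is not re-infused has no scheduled adverse event review after Month 6

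*Combined protocol and SAP*

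**What the plan says.** Addendum B, section B.14.6: "The Month 12 visit will be waived if screening visits for subsequent infusions take place prior to this visit". Addendum C, section C.15.6, has the same rule: "The Month 12 visit will be waived, if screening visits for subsequent infusions take place prior to this visit". Section C.15.1 ties the waiver to the start of re-screening: "at which point the month 12 phone call visit from the original infusion will be waived".

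Section B.14.1, Table B1 key item 12 and Table C1 key item 11 use the same trigger but leave discretion: "Month 12 follow-up phone call may be waived if the subject has a screening visit for an additional infusion prior to this visit".

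In Tables B1 and C1 the row "Review Adverse Events" is ticked on Day 1 and at Months 1, 3, 6 and 12. It is blank at Screening and Baseline. The Screening column does include "Full Medical History", physical examination, ECG, concomitant medications, urinalysis and laboratory tests.

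The Investigational Plan in the synopsis says that all subjects, apart from those participating in Addendum C, "will also have a final twelve-month contact for assessment of vital status and occurrence of hospitalization". The synopsis text on duration is looser: Month 12 applies to Addendum B only where applicable, and to Addendum C as an and/or alternative.

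**The concern.** The condition for the waiver is that screening has taken place. That is harmless for a subject who goes on to the next infusion, because adverse event review resumes on the new Day 1. It is not harmless for a subject who re-screens and then fails or declines. Section C.15.2 enrols subjects only once screening has shown that they remain eligible, so this subject enters no new visit schedule, and the last contact of the old one has been waived. No section brings it back.

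The reasons for failing include new serious comorbid illness, malignancy, abnormal laboratory values and limited life expectancy (C.4.2). The lost follow-up may therefore be related to outcome. One-year survival is named in the secondary objectives of both addenda (B.2.1.2, C.3.1.2), and death from any cause is a secondary endpoint (B.2.2.2, C.3.2.2). A twelve-month vital-status contact is the natural source for both.

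**Working it through.** There is no figure in the plan to reproduce. The check is calendar arithmetic on the stated visit days.

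**Inputs.** Month 6 is Day 180 ± 30 and Month 12 is Day 365 ± 14 (Tables B1 and C1). Screening to baseline takes up to 45 days (B.14.1, C.15.1). Baseline to infusion takes up to four weeks, or 28 days (B.14.2, C.15.2). Re-screening begins within two weeks either side of the Month 12 call (B.14.1, C.15.1). Infusions are 6 to 18 months apart (C.1, C.2, C.5).

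**Subject who is re-infused.** The next adverse event review is the new Day 1, at most 45 + 28 = 73 days after screening starts. The waiver costs little.

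**Subject who re-screens and is not re-infused: gap in adverse event review.** The last ticked review is Month 6. The nominal gap to Month 12 is 365 − 180 = 185 days, and 185/365 = 51% of the year. With visit windows the shortest gap is (365 − 14) − (180 + 30) = 141 days and the longest is (365 + 14) − (180 − 30) = 229 days.

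**Same subject: gap in contact of any kind.** The re-screening visit is itself a contact, so the uncovered time before Day 365 is 365 minus the later of Day 180 and the re-screening day:

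| Re-screening day | Last scheduled contact | Days uncovered to Day 365 |
|---|---|---|
| 107 | 180 (Month 6) | 185 |
| 180 | 180 | 185 |
| 210 | 210 | 155 |
| 270 | 270 | 95 |
| 351 | 351 | 14 |

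A subject who reaches the baseline visit and stops there has that visit as the last contact. It carries no adverse event tick either.

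**Which row applies depends on two timing rules that disagree.** Under the two-week window, screening starts no earlier than Day 365 − 14 = 351, which leaves 14 days to Day 365, or 28 to the end of the window at Day 379. But an infusion at six months could be preceded by screening as early as Day 180 − 73 = 107. If screening cannot start before Day 351, no re-infusion can take place before about 351/365 × 12 = 11.5 months, and the lower part of the 6 to 18 month range cannot be used.

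**Synopsis against B.14.6.** An Addendum B subject who fails screening for Addendum C is never enrolled there, so it is unclear that the synopsis exemption covers that subject. B.14.6 nevertheless removes the contact. For Addendum C the inconsistency runs the other way: the synopsis exempts these subjects, while Table C1 and C.15.6 schedule the call.

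**The case against.** A reader might infer that such a subject has no safety contact at all after Month 6. The documents do not support that as a general statement. A re-screening visit after Month 6 is a scheduled contact with history, examination, ECG and laboratory tests. Sections 8.8, 8.12 and 8.14 would have clinically significant findings recorded, ongoing events reviewed at later contacts, and all adverse events in the trial collected. Often the illness that causes the failure is what the visit detects. This part of the objection stands. What is missing is a ticked adverse event review at that visit and any contact after it.

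Section 4.4 asks that withdrawn subjects be encouraged to return for all remaining assessments. This helps only in part: it does not reinstate an assessment that has been waived. Section C.1 adds, for those who decline, "Subjects that do not want an additional infusion will not be eligible to continue in the study"; that sentence goes on to further infusions under the addendum and does not mention the Month 12 call.

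It is also fair to say that the waiver is discretionary in three places, that Addendum C is exempted in the synopsis, and that under the two-week window the uncovered time is short. These points narrow the concern, chiefly to Addendum B. They also show that the text needs reconciling.

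**Conclusion.** The point holds, mainly for Addendum B. As written in B.14.6, C.15.1 and C.15.6, a treated subject who re-screens before Month 12 and is not re-infused has no scheduled adverse event review after Month 6. That subject also has no scheduled contact after the later of Month 6 and the re-screening (or baseline) visit. The uncovered time before Day 365 is about 14 days on one timing rule and up to 185 days on the other.

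The one-month primary endpoint and the 30-day monitoring are not affected. The loss falls on late adverse events, death from any cause and the exploratory 1-year survival objective.

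A reader might go further and infer a measurable downward bias in late harm. The documents do not support a figure. Up to 20 Addendum B subjects and the pilot subjects returning under Addendum C (12 had received two infusions) could be exposed, but no re-screen failure rate or late event rate is given. The only available scale is per subject: in Addendum B at its full 20, each unknown twelve-month status widens the best-case to worst-case range for 1-year survival by 1/20, or 5 percentage points.

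**What to change.** Make the waiver in B.14.1, B.14.6, C.15.1, C.15.6, Table B1 key item 12 and Table C1 key item 11 depend on the next infusion having been given. A subject who re-screens but is not re-infused then keeps the Month 12 call. Tick adverse event review at the re-screening visit in both tables, and attribute the events found there to the preceding infusion.

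Reconcile three further matters: 'will' against 'may' in the waiver; the synopsis (the twelve-month contact, the Addendum C exemption and the undefined 'if applicable') against the visit schedules; and the two-week re-screening window against the 6 to 18 month infusion interval. Which timing rule applies is for the sponsor to settle.

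The cost is wording, one tick in each of two tables, and a few extra phone calls: at most one per re-screened subject per course, using a script the protocol already provides for.
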